9.1. Data Reporting

The SKCCC Compliance Monitoring Program will provide external monitoring for JHU-affiliated sites in accordance with SKCCC DSMP (Version 6.0, 02/21/2019). The SMC Subcommittee will determine the level of patient safety risk and level/frequency of monitoring.

The PI is responsible for monitoring the study. Data must be reviewed to assure the validity of the data, as well as the safety of the subjects. The PI will also monitor the progress of the trial, review safety reports, and clinical trial efficacy endpoints and to confirm that the safety outcomes favor continuation of the study. The PI will be responsible for maintaining the clinical protocol, reporting adverse events, assuring that consent is obtained and documented, reporting of unexpected outcomes, and reporting the status of the trial in the continuing renewal report submitted to the IRB and to the monitoring review group. The report should be submitted in a timely manner according to the schedule defined by the Johns Hopkins Medicine Institutional Review Board.

9.2. Management of Safety Data

This Study has been designated as an interventional study. As such, all adverse events/product quality complaints for study drug (flotetuzumab) regardless of causality and special situations will be reported from the time a subject has signed an Informed Consent Form (ICF) until 30 days after the last dose of study drug excluding those from subjects not exposed to study drug.

Serious adverse events will be reported for 30 days after the last dose of study drug.

9.3. Adverse Event Definition

An adverse event is any untoward medical occurrence in a clinical study subject administered a medicinal (investigational or non-investigational) product. An adverse event does not necessarily have a causal relationship with the treatment. An adverse event can therefore be any unfavorable and unintended sign (including an abnormal finding), symptom, or disease temporally associated with the use of a medicinal (investigational or non- investigational) product, whether or not related to that medicinal (investigational or non-investigational) product. (Definition per International Conference on Harmonisation [ICH])

This includes any occurrence that is new in onset or increased in severity or frequency from the baseline condition, or abnormal results of diagnostic procedures, including laboratory test abnormalities (except Grade 1 and 2 hematologic and metabolic abnormalities) that are deemed clinically significant by the principal investigator.

This study will utilize the Common Terminology Criteria for Adverse Events (CTCAE) version 5.0 for adverse event reporting, except for IRR/CRS, which has been defined in Table 4. In cases where CTCAE version 5.0 cannot be applied to the toxic event, the investigator will quantify the toxicity based on the intensity as defined:

1. Mild: The subject is aware of the signs or symptoms but they are easily tolerated; usually does not require additional therapy or discontinuation of study drugs.
2. Moderate: The signs and symptoms are sufficient to restrict but do not prevent usual activity; possibly requires additional therapy but usually does not require discontinuation of the study drug.
3. Severe: The subject is unable to perform usual activities and usually requires discontinuation of the study drug.

Patients are to be followed for adverse events for 30 days after the last dose of the study drug and any adverse event occurring in a patient up to 30 days after stopping the study drug or until the start of a subsequent systemic anticancer therapy, if earlier, must be reported. The surveillance period after study drug discontinuation may be extended if there is a strong

suspicion that the drug has not yet been eliminated or if the nature of a particular event may suggest long-term effects from the investigational drug, as assessed by the investigator.

9.4. Serious Adverse Event (SAE) Definition

A serious adverse event based on ICH and EU Guidelines on Pharmacovigilance for Medicinal Products for Human Use is any untoward medical occurrence that at any dose:

- Results in death
- Is life-threatening (The subject was at risk of death at the time of the event. It does not refer to an event that hypothetically might have caused death if it were more severe.)
- Requires inpatient hospitalization or prolongation of existing hospitalization
- Results in persistent or significant disability/incapacity
- Is a congenital anomaly/birth defect
- Is a suspected transmission of any infectious agent via study drug
- Is medically important determined by the investigator(s)*

*The investigator should exercise medical and scientific judgment in deciding whether expedited reporting is also appropriate in other situations, such as important medical events that may not be immediately life threatening or result in death or hospitalization but may jeopardize the subject or may require intervention to prevent one of the other outcomes listed in the definition above. These should usually be considered serious.

NOTE: DEATH FOR ANY REASON SHOULD BE REPORTED AS A SERIOUS ADVERSE EVENT.

9.4.1. Hospitalization or prolongation of existing hospitalization following the completion of flotetuzumab

For reports of hospitalization, it is the sign, symptom or diagnosis which led to the hospitalization that is the serious event for which details must be provided. In the event of prolongation of an already existing hospitalization, the event that triggered the increased hospital stay will be considered as SAE.

Any event requiring hospitalization or prolongation of hospitalization that occurs during the study must be reported as a serious adverse event, except hospitalizations for the following:

- Hospitalizations not intended to treat an acute illness or adverse event (e.g., social reasons such as pending placement in long-term care facility)
- Surgery or procedure planned before entry into the study. [Note: Hospitalizations that were planned before the start of data collection and where the underlying condition for which the hospitalization was planned has not worsened will not be considered serious adverse events. Any adverse event that results in a prolongation of the originally planned hospitalization is to be reported as a new serious adverse event.]
- The investigator will be required to hospitalize the subject for the duration of the treatment period.

9.4.2. Life-Threatening Conditions

An AE or SAE is considered “life-threatening” if, in the view of the Investigator, its occurrence places the subject at immediate risk of death. It does not include an AE or SAE that, had it occurred in a more severe form, might have caused death.

Disease progression should not be recorded as an adverse event or serious adverse event term; instead, signs and symptoms of clinical sequelae resulting from disease progression/lack of efficacy will be reported if they fulfill the serious adverse event definition.

9.5. Unexpected (unlisted) Adverse Event/Reference Safety Information

An adverse event is considered unexpected if the nature or severity is not consistent with the applicable product reference safety information. For a medicinal product(s) with a marketing authorization, the expectedness of an adverse event will be determined by whether or not it is listed in the applicable product information.

For flotetuzumab, the expectedness of an adverse event will be determined by whether or not it is listed in the Investigator’s Brochure. Any unexpected clinical event, regardless of grade requires expedited reporting to the regulatory authorities.

9.6. Adverse Drug Reaction and Toxicity Monitoring

The study team (research nurse, study coordinator or attending) will assign toxicity scores using the NCI Common Terminology Criteria for Adverse Events (CTCAE) version 5.0, weekly through the first cycle of therapy and at least every cycle thereafter. A copy of the CTCAE version 5.0 is available at

https://ctep.cancer.gov/protocoldevelopment/electronic_applications/docs/ctcae_v5_quick_refer

[ence_5x7.pdf](#)). If unexpected and serious toxicity occurs that would result in patients being subjected to unacceptable risk, the trial will be placed on hold while the toxicity is investigated.

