6.2.2. Infusion-related Reaction

Infusion-related reaction including cytokine release syndrome (CRS), which may be life-threatening or fatal, occurred in 81% of patients receiving flotetuzumab. The majority of these reactions were mild to moderate in severity, whereas 8% of patients treated at the RP2D experienced at least one severe (Grade 3) event. None of these events have been life threatening or fatal. Infusion reactions may be clinically indistinguishable from manifestations of

CRS. This typically occurs during the initial 48 hours of the first infusion of flotetuzumab. Symptoms of infusion-related reactions including CRS may include chills, fever, headache, fatigue, flushing, nausea, bronchospasm, and hypotension. Patients should be closely monitored for signs or symptoms of these events. For all patients receiving inpatient flotetuzumab infusion, vital signs should be monitored according to the inpatient standard-of-care. Management of these events may require either temporary interruption or discontinuation of flotetuzumab as described in Section [4.5.1](#).

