8.2. Study Design

This study proposal will be a phase 1 trial of flotetuzumab in patients with relapsed/refractory AML following alloHSCT. The first part of the study will be a dose escalation following a 3+3 design for post-transplant flotetuzumab. The study will start with the recommended dose of flotetuzumab in relapsed/refractory ALL (DL1). The first three patients will be enrolled and monitored for the first cycle of treatment for DLTs through the full DLT period (90 days) before enrolling additional patients. If less than 2 patients experience a DLT, an additional 3 patients will be enrolled. If 0 or 1 out of 6 patients have a DLT, then the dose will be deemed safe and considered the MTD of flotetuzumab in the post-transplant setting. If 2 or more of the first 3 or 6 patients experience a DLT, then the trial will proceed to enroll patients at DL-1 starting with 3 patients. The first three patients on DL-1 will be enrolled and monitored in the first cycle of treatment for DLTs through the full DLT period (90 days) before enrolling additional patients. If less than 2 patients experience a DLT at DL-1, an additional 3 patients will be enrolled at DL-1. If 0 or 1 out of 6 patients have a DLT at DL-1, then the dose will be deemed safe and the MTD. If 2 or more of the first 3 or 6 patients experience a DLT, then the trial will be stopped. An expansion cohort of 4 subjects will be also pursued at MTD for flotetuzumab to further characterize safety, tolerability and any preliminary signs of biological or clinical activity in this cohort. DLT monitoring will continue in this expansion cohort, and the trial will be stopped if two additional subjects experience a DLT. Any patient who discontinues treatment prior to the completion of one cycle of flotetuzumab for disease progression or for an adverse event that is not possibly, probably, or definitely due to the study treatment will be replaced.

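### No rule explicitly pauses accrual after a treatment-related death: the only trial-level hold depends on an expectedness call that the plan leaves open for fatal CRS

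*Combined protocol and SAP*

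**What the plan says.** Trial-level action on safety comes from two places.

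- **Section 9.6, the hold.** "If unexpected and serious toxicity occurs that would result in patients being subjected to unacceptable risk, the trial will be placed on hold". The hold lasts pending an investigation. Three conditions must be met: unexpected, serious, and an unacceptable risk.
- **Section 8.2, the DLT counts.** At DL1, "If 0 or 1 out of 6 patients have a DLT, then the dose will be deemed safe and considered the MTD". Two or more DLTs in the first three or six patients lead to DL-1, and two or more at DL-1 stop the trial. In the four-patient expansion, "DLT monitoring will continue in this expansion cohort, and the trial will be stopped if two additional subjects experience a DLT". Accrual waits for the 90-day DLT period after the first three patients at each dose level.

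Expectedness is defined in 9.5. The general rule is: "An adverse event is considered unexpected if the nature or severity is not consistent with the applicable product reference safety information". For flotetuzumab, "the expectedness of an adverse event will be determined by whether or not it is listed in the Investigator’s Brochure". On CRS, 6.2.2 says: "Infusion-related reaction including cytokine release syndrome (CRS), which may be life-threatening or fatal, occurred in 81% of patients receiving flotetuzumab". The same section adds that none of these events has been life-threatening or fatal.

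Section 6.2.1 makes related non-hematologic toxicity of Grades 3 to 5 a DLT, as a single category. Non-leukemia death within 90 days of starting treatment appears as the last bullet of the list that follows the word EXCEPT. Table 6 has a row for CRS resulting in death; its only actions are to notify the regulatory authorities and report an SAE.

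**The concern.** Section 2.10 says that flotetuzumab has not been specifically studied in AML after transplant. A drug-related death there is the event after which one would most want enrolment to stop while the case is examined. The plan foresees fatal CRS in 6.2.2, in the dilution warning of 6.1 and in a row of Table 6, yet none of these states what happens to accrual. That is left to a hold whose first condition, unexpectedness, is hard to apply to the drug's best-known severe toxicity. If the death is classed as expected, or the risk is not judged unacceptable, 9.6 does not apply. Section 8.2 then directs the next patients to be enrolled as after any other single DLT. The placement of the death bullet in 6.2.1 adds doubt about whether some deaths enter the DLT count at all.

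**Working it through.** **1. Sample-size structure (reproduces the plan's figures).** One dose level: 6 + 4 = 10, the N of Table 7. Both levels plus expansion: 6 + 6 + 4 = 16, the maximum in 8.3.1. The plan gives no operating characteristics and no threshold specific to deaths.

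**2. What the counts permit.** Take a related death as one DLT, under the Grade 3–5 criterion.
- One death in six: the dose is accepted. Observed rate 1/6 = 17%, exact 95% CI 0.4% to 64%.
- One more in the expansion of four: no stop. Observed rate 2/10 = 20%, exact 95% CI 2.5% to 56%.

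**3. Does the 9.6 hold fill the gap for a CRS death?**
- For unexpected: 9.5 includes severity, and 6.2.2 reports no life-threatening or fatal case.
- For expected: 9.5 then makes listing in the Investigator's Brochure decisive for flotetuzumab, and 6.2.2 itself describes CRS as potentially fatal.

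The Brochure is not part of the documents, so the text allows either answer.

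**4. What the 90-day wait covers.** A death among the first three patients at a dose level falls inside a period in which patients 4 to 6 cannot be enrolled. The wait does not stagger patients 1 to 3, patients 4 to 6 or the expansion. It also requires no review of the death before enrolment resumes.

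**5. The list in 6.2.1.** If the last bullet belongs to the exceptions, a CRS death within 90 days is a DLT under the Grade 3–5 criterion and exempt under the bullet. If it was meant as a separate DLT criterion, the conflict disappears. The text does not settle which.

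**6. Illustrative probabilities.** Let f be the related-death rate per patient. It is an assumption, because the documents give none for this setting. Assume also no other DLTs and that each death counts as one DLT. The probability that DL1 is accepted, the expansion completes and at least one of the ten patients has a related death is

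P(X₆ ≤ 1) × P(X₄ ≤ 1) − (1 − f)¹⁰, with X₆ and X₄ binomial.

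| f | P(X₆ ≤ 1) | P(X₄ ≤ 1) | Product | (1 − f)¹⁰ | Result |
|---|---|---|---|---|---|
| 0.02 | 0.9943 | 0.9977 | 0.9920 | 0.8171 | 17.5% |
| 0.05 | 0.9672 | 0.9860 | 0.9537 | 0.5987 | 35.5% |
| 0.10 | 0.8857 | 0.9477 | 0.8394 | 0.3487 | 49.1% |

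For scale, 6.2.3 reports no Grade 5 treatment-related event in 66 patients. The two-sided exact 95% upper limit is 1 − 0.025^(1/66) = 5.4%, from a different population.

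**7. Sensitivity to other DLTs.** If patient 1 has a fatal DLT, DL1 is still accepted only if the other five have none: (1 − p)⁵ = 59%, 33% and 17% for DLT rates p of 10%, 20% and 30%.

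**The case against.** A reader might infer that a CRS death triggers no pause at all. The documents do not support that. Under the severity limb of 9.5, a fatal case could be classed as unexpected, since 2.9 and 6.2.2 report nothing above Grade 3 at the recommended dose and 6.2.3 lists no Grade 5 event. The 9.6 hold would then be available. The 90-day wait is itself a pause for part of each first cohort. A death that is the second DLT leads to de-escalation or stopping.

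There is other oversight too. Every death is an SAE (9.4), the IRB is notified (9.7), and the investigator must confirm that safety outcomes favor continuing (9.1). Section 9 also adopts an institutional monitoring plan that is not reproduced and may or may not address deaths. None of these, as written here, is an automatic hold.

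Equal weighting of DLTs is normal for a 3+3 and is not an error. The no-other-DLT assumption is the one that most favors the concern: GVHD during treatment and many related Grade 3–4 events are DLTs, so the true probability of passing all counts after a death would be lower. Rates above about 5% also exceed the limit from 0/66.

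What remains is narrower: pausing after the gravest event depends on a contestable classification and a separate risk judgement.

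**Conclusion.** The concern holds in limited form. No passage explicitly pauses accrual after a treatment-related death, and whether a CRS death meets the 9.6 hold is left open. Taking a related death as one DLT, up to one in the first six patients and one more in the four-patient expansion passes every count rule. The status of non-leukemia death in 6.2.1 must be reconciled with the Grade 3–5 criterion; read literally, the exception would weaken even the count rules.

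The structural gap rests on the text alone. The probabilities, about 17% at f = 0.02 and 35% at f = 0.05, are illustrations under assumed death rates with no other DLTs; they are not predictions. The Investigator's Brochure or the institutional monitoring plan could narrow the gap, but neither can be credited or excluded from these documents.

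**What to change.** Reconcile 6.2.1, the death row of Table 6, 8.2, 9.5 and 9.6 so that:

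1. The DLT status of a related death, and of a non-leukemia death within 90 days, is unambiguous.
2. The existing 9.6 hold on enrolment, pending investigation, applies to any death at least possibly related to flotetuzumab without depending on the expectedness call. Review would run through the investigator and the monitoring plan already named in Section 9, with the decision to resume documented.
3. Section 8.2 cross-refers to that hold, so that its directions to enrol further patients are read subject to it.

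DLT thresholds, doses and patient-management rules stay as they are. The cost is a few sentences in an amendment and, only if such a death occurs, a short pause in accrual. If operating characteristics are added, show them over a range that includes low death rates and state what is assumed about other DLTs.

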9.7. Toxicity Reporting

The Principal Investigator is responsible for ongoing safety evaluation of the study. The Principal Investigator is required to notify his/her Institutional Review Board (IRB) of a serious adverse event according to institutional policy. The requirements for IRB Protocol Problem Reporting at Johns Hopkins are can be found at this website:

http://www.hopkinsmedicine.org/institutional_review_board/guidelines_policies/guidelines/

FDA reporting requirements

7 Calendar-Day IND Safety Report

Fatal or life threatening SAEs that meet the criteria for reporting to the FDA must be reported to the FDA within 7 calendar days after awareness of the event. Serious adverse events (SAEs) that are unexpected, and at least possibly associated to the study drugs, as assessed by the Investigator, should be reported promptly to the Food and Drug Administration (FDA).

15 Calendar-Day Written IND Safety Report

The Investigator is required to notify the FDA, and all participating investigators in a written IND Safety Report, of any serious, unexpected adverse event considered by the Investigator to be possibly related to the use of study drugs within 15 calendar-days of first learning of the event. If applicable, the Investigator must also notify the FDA, and all participating investigators, of any finding from tests in laboratory animals that suggests a significant risk for human subjects including reports of mutagenicity, teratogenicity, or carcinogenicity within 15 calendar-days of first learning of the event.

All other SAEs that meet the criteria for reporting to the FDA must be reported to the FDA within 15 calendar days after awareness of the event. A clear description of the suspected reaction should be provided along with an assessment as to whether the event is drug or disease related.

All IND safety reports must be submitted to the FDA on Form 3500A and be accompanied by Form 1571. The report must be submitted to an appropriate Review division that has the responsibility to review the IND application under which the safety report is submitted. All IND

safety reports are recommended to be submitted electronically. Other means of rapid communication to the respective review divisions Regulatory Project Manager (e.g., telephone, facsimile transmission, email) may also be used.

Reporting Protocol Deviations to the JHM IRB

There are several types of deviations from protocol procedures recognized by the JHM IRB, and each type has a different IRB reporting requirement:

A. Protocol deviations that constitute unanticipated problems involving risks require prompt reporting to the JHM IRB: A protocol deviation that constitutes an “unanticipated problem involving risks to subjects or to others” (Policy No. 103.6(b) for the definition of an unanticipated problem) must be reported promptly to the IRB, as follows:

1. Emergency deviations: When a deviation occurs in an emergency situation, such as when a departure from the protocol is required to protect the life or physical well-being of a participant. The Sponsor (JHU Principal Investigator) and the reviewing IRB must be notified as soon as possible, but not later than 5 days after the emergency situation occurred (21 CFR 812.150(a)(4)).
2. Major, non-emergent deviations without prior approval: A planned deviation that is non-emergent and represents a major change in the protocol as approved by the IRB. The Principal Investigator and the IRB must approve the request before the proposed change is implemented. If a major, non-emergent deviation occurs without prior IRB approval the event is considered non-compliance. Noncompliance must be reported to the IRB promptly.

B. Protocol deviations that are only minor or administrative: At JHM, minor or administrative protocol deviations are defined as those which do not “affect the scientific soundness of the research plan or the rights, safety, or welfare of human subjects.” If a protocol deviation occurs which meets this definition, the deviation should be reported to the JHM IRB at the time the continuing review application is submitted. Examples of minor or administrative deviations could include: follow up visits that occurred outside the protocol required time frame because of the participant’s schedule, or blood samples obtained at times close to but not precisely at the time points specified in the protocol.

